7.3.3 Serious Adverse Events (SAEs)

A **serious AE (SAE)** is any untoward medical occurrence that at any dose:

- results in death,
- is life-threatening (see below),
- requires hospitalization or prolongation of existing hospitalization,

- results in persistent or significant disability/incapacity,
- is a congenital anomaly/birth defect,
- is another important medical event.

NOTE: The term 'life-threatening' refers to an event in which the subject was, in the view of the reporting Investigator, at immediate risk of death at the time of the event; it does not refer to an event which may hypothetically have caused death had it been more severe.

In deciding whether an AE/ADR is serious, medical judgment should be exercised. Thus, important AEs/ADRs that are not immediately life-threatening or do not result in death or hospitalization, but may jeopardize the subject or may require intervention to prevent one of the other outcomes listed in the definitions above, should also be considered serious.

In addition, although not classified under the seriousness criteria, all suspected transmissions of an infectious agent should be reported as SAE. A suspected virus transmission means that virus antigen has been detected in the subject. A passive transmission of antibodies alone does not constitute a suspected virus transmission.

7.3.3.1 SAE Reporting Timelines

All SAEs, whether or not they are suspected to be related to study treatment, are to be reported immediately by telephone, fax, or email to the Clinical Project Manager or designee with the contact details provided to each site in the Investigator Site Binder. The contact details will also be communicated at the study initiation visit.

In addition, within 24 hours after recognition of the event, an Octapharma Serious Adverse Event Report must be completed and submitted to:

Octapharma's Corporate Drug Safety Unit

OCTAPHARMA Pharmazeutika Produktionsges.m.b.H.

[name]

████████████████████
██
24 hours emergency telephone numbers:

████████████████████
████████████████████
The Investigator must update the Octapharma Serious Adverse Event Report as soon as any additional information becomes available. The Investigator must also report SAEs to the IRB/IEC as required by local and national laws. The Investigator must maintain documentation of all communications to and from the IRB/IEC.

In accordance with 21 CFR 312.32 and local authorities, the Sponsor will submit to the FDA unexpected adverse reactions within 15 calendar days. Unexpected fatal or life-threatening adverse reactions will be submitted within 7 calendar days.

7.3.3.2 Waivers from SAE Reporting Requirement

Waivers from the SAE reporting requirement include surgeries that are elective or were planned before study entry or prolongations of existing hospitalizations for economic or social, but not medical, reasons. Such surgeries or prolongations of hospitalizations should not be considered SAEs.

7.3.4 Laboratory Safety Evaluations

The following laboratory parameters will be investigated during the study at the time points specified in Table 1: Flow Chart of Assessments and below.

All laboratory assessment will be performed at the local laboratories for each study site. In Russia and Ukraine, a central local laboratory could be used for all or part of the tests depending on the site facilities. Samples will be drawn prior to IMP infusions on Day 1 through Day 4, if appropriate:

Laboratory Measures at Screening:

- Comprehensive Metabolic Panel (CMP)
- Complete blood count (CBC) with differential
- D-Dimer
- Fibrinogen
- Prothrombin time (PT), partial thromboplastin time (PTT), international normalized ratio (INR)
- hsCRP
- Erythrocyte sedimentation rate (ESR)
- Ferritin, lactic acid dehydrogenase (LDH)
- Cytokines (IL-1Beta, IL-6, TNF-alpha, IFN-gamma)
- C3, C4, CH50
- Total CK, CK-MB fraction, myoglobin
- High sensitivity Troponin I (hs-cTnI) or cTnI-ultra
- Serum pregnancy
- Blood culture
- Urine legionella, pneumococcal antigens

Laboratory measures for Day 1 through Day 3 (If less than 8 hours between Screening lab draw and Baseline Day 1, Baseline labs do not need to be redrawn):

- BUN
- Serum creatinine
- Sodium
- Potassium
- D-Dimer
- Arterial Blood Gases (Day 1 only)

Laboratory measures for Day 4:

- BUN
- Creatinine
- Sodium
- Potassium
- PT, PTT, INR
- CBC with differential
- D-Dimer

Laboratory measures for Day 7:

- CMP
- ESR
- Fibrinogen
- PT, PTT, INR
- CBC with differential
- hsCRP
- D-Dimer
- Ferritin, LDH
- Arterial Blood Gases (for patients with a clinical status of 3 or 4)

Laboratory measures for Day of Discharge (only if discharge is after Day 7) or Day 33, whichever is sooner:

- CMP
- CBC with differential

- hsCRP
- Cytokines (IL-1Beta, IL-6, TNF-alpha, IFN-gamma)
- C3, C4, CH50
- Total CK, CK-MB fraction, myoglobin
- D-Dimer
- Ferritin, LDH
- High sensitivity Troponin I (hs-cTnl) or cTnl-ultra
- PT, PTT, INR
- Fibrinogen

The methods of determination and normal ranges for each parameter will be provided in the clinical study report.

7.3.5 Vital Signs and Physical Examination

Vital signs measurements, blood pressure, pulse, respiration rate, and body temperature (°C) will be recorded as indicated in Table 1: Flow Chart of Assessments.

Routine complete physical examination will be performed at the visits specified in Table 1: Flow Chart of Assessments. Any clinically significant worsening, as deemed by Principal Investigator, or new abnormality found during the exam will be documented as an AE.

7.3.6 Chest CT/Chest X-ray

A non-contrast Chest CT or Chest X-ray will be performed at Screening and Day 7 to assess clinically significant changes from Baseline (Day 1) as determined by the Investigator.

7.3.7 Other Relevant Safety Information

a) *Post-study related safety reports*

Any SAE which occurs up to 4 weeks after the last IMP administration should be reported by the Investigator to the Sponsor in case the Investigator becomes aware of it. Proactive monitoring for post-study SAEs is not required.

In case a post-study SAE is identified, the Investigator should complete an SAE form and state the relation to the clinical study in the report.

Deaths occurring within 4 weeks after the last IMP administration should also be reported, regardless of whether or not they are considered treatment-related.

b) Pregnancies

Every effort will be made to avoid pregnancy during the use of an IMP. Pregnancies occurring during the study (fetal exposure to the IMP) need to be reported.

In case of pregnancy during the study, the Investigator should complete the Pregnancy Notification Form and send or fax it to the Clinical Project Manager or designee (see Section 7.3.3.1).

Follow-up information on the outcome of both mother and fetus will be requested by a Sponsor representative.

c) Overdose, interaction, medication error, and lack of efficacy

The following safety relevant information should be reported as AE or, if the reaction fulfills one of the criteria for seriousness, as SAE.

d) Drug overdose

An overdose is a deliberate or inadvertent administration of a treatment at a dose higher than specified in the protocol and higher than the known therapeutic dose that is of clinical relevance. The reaction must be clearly identified as an overdose.

e) Drug interaction

A drug interaction is a situation in which a substance or medicinal product affects the activity of an IMP, ie, increases or decreases its effects, or produces an effect that none of the products would exhibit on its own. The reaction must be clearly identified as a drug interaction.

f) Medication error

A medication error involves the inadvertent administration or unintended use of a medicinal product which may be caused by the naming, presentation of pharmaceutical form/packaging, or instructions for use/labelling. The reaction must be clearly identified as a medication error.

g) Lack of efficacy

Lack of efficacy is suspected when the therapeutic result is not as expected.

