5.4 Dose and Dosing Schedule

Octagam 10% is available in glass bottles with different volumes of human immunoglobulin. Glass bottles of different volume should be combined in order to reach the required amount of IgG.

Octagam 10% or placebo will be administered by intravenous infusions on 4 consecutive days. The amount of *Octagam 10%* calculated on the dosage delivery schedule is 2 g/kg divided evenly over 4 days (0.5 g/kg/day).

If a subject is randomized to receive placebo, the same volume with the same infusion rate as would have been applied in case the subject would have been randomized to

2.0 g/kg *Octagam 10%* will be used. Therefore, they will receive an equal dose of placebo given over 4 days.

Body weight is to be measured at Screening or within 24 hours of first IMP administration and reported to the pharmacist or designee as it is needed for the preparation of the following study medication dosages.

All subjects should be clinically assessed for being adequately hydrated prior to IMP administration. TEE prophylaxis should be considered.

The initial infusion rate for each infusion episode will be:

- 0.01 mL/kg/min (60 mg/kg/h) for the first 30 minutes (\pm 5 minutes)
- if tolerated, advanced to 0.02 mL/kg/min (120 mg/kg/h) for the next 30 minutes (\pm 5 minutes)
- if tolerated, advanced to 0.04 mL/kg/min (240 mg/kg/h) for the remainder of the infusion

The interval of 30 minutes may be prolonged as per discretion of the investigator.

In subjects at risk for thromboembolic adverse reactions and acute renal failure (such as advanced age, hypertension, history of thrombotic episodes, subjects with prolonged periods of immobilization, concomitant nephrotoxic medication, diabetes mellitus, overweight, hypovolemia), *Octagam 10%* should be administered at the minimum rate of infusion practicable.

If AEs occur during the infusion, the rate is to be reduced to half the rate at which the event occurred, or the infusion is to be interrupted until symptoms subside. The infusion may then be resumed at a rate tolerated by the subject. In case of severe hypersensitivity or anaphylaxis, the infusion will not be restarted and all treatment with the IMP will be withdrawn. The subject will continue to be followed up in accordance with study-specific procedures as specified in the protocol with the exception that no further administrations of IMP will be performed. The subject will receive ongoing treatment in accordance with local SOC.

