6.1.8 Time Windows Used in this Study, Including Tolerances

In this study, the following time windows and tolerances apply:

Table 2: Time Windows Used in this Study

Time point	Time stated	Tolerance
Screening Visit	24 hours before Visit 1	Max of 26 hours
Visits 1 to 4	Day 1 to 4	None
Visit 5	Day 7 or discharge day	± 1 day
Visit 6 and 7	Days 14 and 21	± 2 days
End of Study Visit	Day 33	± 3 days
Q3 month post-study follow-up	Every 3 months after completion of core trial or early termination	± 14 days

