## 1. Introduction

This statistical analysis plan (SAP) expands the analysis plan in *Section 9 Statistical Methods and Sample Size* of the study protocol “Efficacy and Safety of Octagam 10% Therapy in COVID-19 Patients with Severe Disease Progression” authored by the sponsor (Octapharma Inc) dated January 27, 2021.

Changes to the previously approved SAP are the following:

- The interim analysis has been removed, due to an unexpected acceleration in enrollment. DMC meeting schedules have been described as per actual conduct.
- Secondary endpoints have been updated to reflect the latest protocol version.
- Missing data imputation rules have been revised to allow for the incorporation of additional subject information with respect to establishing the clinical status of a subject at each visit

The scope of analysis provided in this SAP includes: the three scheduled Independent Data Monitoring Committee (IDMC) data reviews and the final analysis after Day 33 of the last subject’s enrollment.

Note that after completion of the core 33-day trial, all subjects will be followed for a one-year period by means of a registry database; subjects will be contacted every 3 months ( $\pm 14$  days) for their health status and any residual health effects from COVID-19 or the study treatment. Analysis of this one-year follow-up registry data is not within the scope of this SAP but will be submitted as a supplement to the core study data once all subjects have completed the year of follow-up.

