Cumulative duration in ICU will be imputed similarly, unless a patient has a useable discharge date (e.g. not occurring prior to prohibited medication use); in this case, the ICU discharge date will be set to the hospital discharge date. If a subject's last assessment identifies that IMV was used (and has no usable end date), the date on which it is no longer used will be assumed Day 33 unless the subject is discharged from the hospital prior to Day 33. If this occurs, the hospital discharge date will be used. IMV end dates will be imputed similarly, assuming that IMV ceases at the time of ICU discharge. Hospitalization, ICU, and IMV end dates for subjects who died prior to Day 33 during these events (e.g. after ICU admission or IMV initiation) will result in assumed end dates of Day 33 for endpoint analyses, so long as prohibited medication was not administered. Any dates on or after the start date of prohibited medication use will be considered unusable for imputation purposes; ongoing hospitalization, ICU, or IMV at the time of medication use will default to extrapolation to Day 33.

For the key secondary endpoint involving severe progression (ECMO, IMV, and death), subjects who withdrew early from study prior to Day 33 without evidence of events will be treated as not having the event. Sensitivity analyses will be conducted (1) treating them as failures (having the event at their last study visit) and (2) excluding them from the analyses. An additional analysis of these endpoints will be provided, treating prohibited medication use prior to Day 33 as an event, as well as allowing for status (event or success) without regard to prohibited medication use.

The outcomes for safety assessment and for additional efficacy analysis as well as exploratory endpoints will not be imputed if data is missing.

Please also refer to the more detailed descriptions in sections 12 to 18 of this SAP for additional details on the handling of missing data for particular endpoints and analyses.

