Mortality rate is defined as the proportion of subjects who have died on or prior to Day 33. For this analysis, subjects who use prohibited medication prior to the earliest of death or Day 33 will not be included in analyses. Hypothesis testing will be performed as described for the primary endpoint.

Key secondary endpoints which demonstrate statistical significance will be analyzed by subgroups including sex (male/female), race, ethnicity, geographic region, and disease severity (according to the definitions in the eCRF). All key secondary endpoints will be analyzed by age using testing analogous (unstratified) testing methodology to the specified analyses. Length of time in ICU from randomization through Day 33 will also be analyzed by baseline ICU status. Sensitivity analyses, using all available data, regardless of prohibited medication usage, will be conducted where applicable. The descriptive analyses for the following other secondary endpoints will be based on the primary efficacy analysis (e.g. CMH) method:

- Proportion of patients whose results of reverse transcription polymerase chain reaction (RT-PCR) for SARS-CoV-2 from nares/throat swab and/or sputum and/or lower respiratory tract sample are “Not Detected” on Day 7
- Proportion of subjects admitted to the ICU from randomization through Day 33
  - Only admittance (new or returning) post-randomization will qualify as an event
  - Analyses will be stratified additionally by baseline ICU status
  - If expected event counts do not satisfy CMH testing criteria, baseline ICU status will be removed from analysis as a first step in analysis update
- Proportion of subjects with improvement on Days 7, 14, 21, 33

- Proportion of subjects requiring IMV by Day 33.

The descriptive analyses for the following, other secondary endpoints will be based on the Kaplan-Meier analysis of length of hospitalization:

- Time to recovery through Day 33 where recovery is defined as a clinical status of 1 or 2
- Time to first improvement in clinical status through Day 33

These secondary endpoints will also be analyzed by age category.

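### Day 33 vital status is not required once a subject leaves the study, and mortality has no withdrawal rule or sensitivity analysis

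*Protocol*

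**What the plan says.** **Endpoint.** SAP 14: "Mortality rate is defined as the proportion of subjects who have died on or prior to Day 33". Protocol 9.2.3.2 has the same definition. The analysis set is ITT, meaning all randomized subjects (Protocol 9.2.2, SAP 6); users of prohibited medication are left out of this analysis. Mortality is sixth of six key secondary endpoints tested in order, and severe progression, which includes death, is fourth.

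**Collection while in the study.** Clinical status, with death as category 6, is assessed through Day 33, by telephone after discharge (Protocol 6.1.5, 6.1.6, 7.2.1). AEs are collected until Day 33 (Protocol Table 1).

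**Reporting after leaving the study.** Protocol 7.3.7(a) is headed as post-study safety reporting. An SAE up to 4 weeks after the last infusion "should be reported by the Investigator to the Sponsor in case the Investigator becomes aware of it". It adds "Proactive monitoring for post-study SAEs is not required". On deaths it says "Deaths occurring within 4 weeks after the last IMP administration should also be reported, regardless of whether or not they are considered treatment-related".

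**Analysis after withdrawal.** For severe progression, SAP 4.1 says "subjects who withdrew early from study prior to Day 33 without evidence of events will be treated as not having the event". Two sensitivity analyses follow: withdrawn subjects counted as having the event, and withdrawn subjects excluded. Protocol 9.2.5 agrees. No equivalent text exists for mortality.

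**Registry.** Table 2 of Protocol 6.1.8 schedules contact "Every 3 months after completion of core trial or early termination". SAP 1 states "Analysis of this one-year follow-up registry data is not within the scope of this SAP".

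**The concern.** Day 33 mortality needs vital status on Day 33 for every subject in the denominator. For a subject who has left the study, for example by withdrawing consent, by non-compliance or through loss to follow-up, the documents contain no instruction to obtain it. A death that nobody reports leaves the subject in the ITT denominator and out of the numerator.

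Unrecorded deaths can only lower an arm's observed mortality. If the number withdrawn, or the risk of death after withdrawal, differs between arms, the comparison is biased as well, in favour of the arm with more hidden deaths. Withdrawal need not be unrelated to outcome. Protocol 4.3.1 lists, as a possible reason for premature termination, a new condition that meets an exclusion criterion, and the exclusion criteria include invasive ventilation. Mortality also informs the benefit-risk assessment, whether or not the testing sequence reaches it.

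**Working it through.** **1. Denominator.** Protocol 9.1 gives 88 evaluable subjects per arm and 15% drop-out by Day 7. Then 88 / 0.85 = 103.5, rounded up to 104 per arm and 208 in total, as the plan states. The drop-out allowance is 104 × 0.15 = 15.6, about 16 per arm.

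**2. Reporting window against the endpoint.** The product is "administered by intravenous infusions on 4 consecutive days" (Protocol 5.4), so the last infusion falls on Day 1 to Day 4. Window end = last infusion day + 28.

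| Last infusion | Window ends | Days uncovered through Day 33 |
|---|---|---|
| Day 1 | Day 29 | 4 |
| Day 2 | Day 30 | 3 |
| Day 3 | Day 31 | 2 |
| Day 4 | Day 32 | 1 |
| Never dosed | not defined | not defined |

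A subject who completes treatment loses one day, so the calendar gap is minor. The larger weakness is that, inside the window too, nobody has to look. Protocol 6.1.2 foresees subjects who are randomized but not dosed, when the investigator judges that dosing adds risk; they stay in the ITT set.

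**3. Withdrawal rules for the key secondary endpoints (SAP 4.1 and 14).**

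| Endpoint | Rule for withdrawn subjects |
|---|---|
| Length of hospital stay | Censored at Day 33 |
| Day 14 clinical status | Imputed as for Day 7 |
| IMV and ICU duration | End date projected to Day 33 if no usable date |
| Severe progression | No event, plus two sensitivity analyses |
| Mortality | None stated |

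Only mortality lacks a rule. Treating withdrawn subjects as alive therefore follows from the definition (a count of recorded deaths over all randomized) and is not an instruction in the text.

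**4. Size within an arm.** Let w be the number per arm with unknown vital status and q the proportion of them who die by Day 33 unrecorded. Understatement = w × q / 104, at most w / 104. Neither document gives w or q, so both are assumptions.

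| w | Maximum (q = 1) | q = 0.10 | q = 0.50 |
|---|---|---|---|
| 2 | 1.9 points | 0.2 | 1.0 |
| 5 | 4.8 | 0.5 | 2.4 |
| 10 | 9.6 | 1.0 | 4.8 |
| 16 | 15.4 | 1.5 | 7.7 |

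**5. Size between arms.** With the same q in both arms, bias in the difference = (w₁ − w₂) × q / 104. For 16 against 8 withdrawn it is 8 × 0.10 / 104 = 0.8 points to 8 × 0.50 / 104 = 3.8 points. With equal numbers and equal risk it is zero.

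**The case against.** The strongest reply is that 7.3.7 is the wrong place to look. It sets a safety-reporting window and is not the source of the mortality endpoint, which comes from clinical status and AE collection through Day 33. A reader might infer that 7.3.7 is the only way a death after stopping treatment can be captured. The documents do not support that. Subjects who stop infusions for severe hypersensitivity (Protocol 5.4) or receive a prohibited product (4.2) stay in follow-up, and withdrawals for an AE are followed until it resolves (6.1.7). A subject never dosed has not thereby left the study. This stands, and it confines the point to subjects who leave the study without such follow-up. Protocol 7.3.2.7 withdraws anaphylaxis cases from the study whereas 5.4 keeps them in follow-up; those passages must be reconciled.

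Three other strong readings also fail:

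- *That the SAP instructs counting withdrawn subjects as alive for mortality.* That rule is written for severe progression, where the two sensitivity analyses already limit the harm.
- *That sites report deaths only if they happen to hear of them.* The awareness condition is in the SAE sentence and is not repeated for deaths. Even so, no search is required for either.
- *That registry information is barred.* SAP 1 excludes analysis of registry data. It does not forbid using a death date that becomes known, and the severe-progression rule does not limit the source of evidence.

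It can also be said that SAP 7 leaves missing-data decisions to the blinded review. That review could supply a rule, but it cannot supply vital status that was never collected.

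**Conclusion.** The point holds for subjects who leave the study before Day 33. No text requires their Day 33 vital status, post-study reporting is passive and stops 1 to 4 days short, and mortality has no withdrawal rule and no withdrawal sensitivity analysis. Severe progression shares the ascertainment weakness but has a rule and two sensitivity analyses.

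The size cannot be determined from the documents. The bound is w/104 per arm: 4.8 points for 5 subjects of unknown status and 15.4 points for 16. The last figure is a ceiling. It treats the whole sample-size drop-out allowance as lost with unknown status and assumes that all of those subjects died unrecorded. A reader might take the 15% allowance as a forecast of missed deaths, or understated mortality as established. Neither follows, because both depend on deaths going unrecorded.

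The primary endpoint is unaffected by the Day 29 to 33 gap, and mortality is last in the hierarchy. This is an inexpensive improvement that should be made, and it is not a defect that undermines the trial.

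**What to change.** 1. **Collection.** Seek vital status and date of death at Day 33 for every randomized subject, including those withdrawn or never dosed, from the hospital record or a Day 33 call, as consent allows.
2. **Protocol 7.3.7.** Extend the death reporting window to the later of Day 33 and 4 weeks after the last IMP administration. This also gives never-dosed subjects a defined window.
3. **SAP 4.1 and 14.** Use this vital status for severe progression and mortality. Allow registry information to update it when available, without delaying the Day 33 analysis. The first registry contact comes about 3 months after early termination, whereas the primary analysis may be run once the last subject has completed Day 33.
4. **Status still unknown.** State the main-analysis rule for mortality explicitly, and apply the two sensitivity analyses already planned for severe progression (counted as event; excluded). A Kaplan-Meier estimate censored at last known alive can be added as supportive only, because it assumes that loss is unrelated to the risk of death.

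The cost is short wording changes in both documents and a few extra chart checks or calls. There will still be no data where a subject refuses all contact and access to records.
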